### **1.3. Schedule of Activities (SoA)**

This section includes the following SoAs:

- Baseline, On-Study and Post-Study Treatment Follow-Up SoA
- Continued Access SoA

Baseline, On-Study and Post-Study Treatment Follow-up SoA														
	Baseline		Cycle = 21 days							Short-Term Follow Up a			Long-Term Follow-Up b	Instructions
	(Day Relative to C1D1)		Cycle 1				Cycle 2		Cycle 3-n	801	802	803	804-X	
			(±3 days)				(±3 days)		(±3 days)	30 day follow-up ±5 days	60 day follow-up ±5 days	90 day follow-up ±5 days	Q90D	
Procedure	≤28	≤7	D1	D2	D8	D15	D1	D2	D1					
Informed consent (Main and Phase 1b Cohort C consent)	X													Main ICF must be signed before any protocol-specific procedures are performed and Phase 1b Cohort C ICF prior to tissue collection for CD73 testing
Inclusion/exclusion criteria	X													
Medical history	X													Including assessment of preexisting conditions and historical illnesses, and habits (such as tobacco and alcohol use).
Cancer treatment history	X													Record prior anticancer therapy
Concomitant medication	X		X							X	X	X		See Section 6.5
Physical examination	X		X		X	X	X		X					Collect weekly during Cycle 1, and then on D1 of every cycle thereafter. A partial physical examination may be performed by a healthcare professional other than the physician on C1D8 and C1D15.
Vital signs	X		See Section 1.3.1.						X	X				Collect weekly during Cycle 1, and then on D1 of every cycle thereafter. Please collect vitals as follows: - At baseline only: Height, - At D1 of every cycle: Weight, - At every schedule visit: Temperature, blood pressure, pulse rate, respiratory rate, and pulse oximetry. Please refer to Section 1.3.1. for detailed collection pertaining to collection on C1D1-C3-n (D1).

Baseline, On-Study and Post-Study Treatment Follow-up SoA															
	Baseline		Cycle = 21 days							Short-Term Follow Up a			Long-Term Follow-Up b	Instructions	
	(Day Relative to C1D1)		Cycle 1				Cycle 2		Cycle 3-n	801	802	803	804-X		
			(±3 days)				(±3 days)		(±3 days)	30 day follow-up ±5 days	60 day follow-up ±5 days	90 day follow-up ±5 days	Q90D		
Procedure	≤28	≤7	D1	D2	D8	D15	D1	D2	D1						
AE collection	X								X					Collect continuously at every visit and throughout the study using CTCAE Version 5.0. During the 30-, 60-, and 90-day follow-up visits, collect all AEs/SAEs. Thereafter, collect only SAEs related to study treatment or protocol procedures	

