## 4. Study Design

### 4.1. Overall Design

Study JZMA is an open-label, multicenter, global, 2-part Phase 1 study of LY3475070 alone or in combination with pembrolizumab in advanced cancer patients.

Phase 1a of the study will target the following tumor types: triple negative breast cancer, pancreatic cancer, PD-1 refractory NSCLC, PD-1 refractory RCC, PD-1 refractory melanoma, metastatic castrate resistant prostate cancer (mCRPC) and ovarian cancer. In **Cohort A** in Phase 1a, escalating doses of single agent LY3475070 will be evaluated in at least 3 evaluable patients per dose level (i.e., DLA1-A4, see Schema in Section 1.2). However, based on the observed PK, pharmacodynamic, and safety data observed, not all provisional dose levels may be explored. Intermediate and/or higher dose as well as alternative schedules of administration (BID dosing) will be explored if deemed necessary after discussion between Lilly and investigators. The dose limiting toxicity (DLT) observation period will be 28 days. The first patient of each DL will be observed for 48 hours before additional patients are enrolled to that DL. The totality of safety data will be reviewed by the Lilly clinical research physician/clinical research scientist (CRP/CRS) and study investigators prior to escalating to a next DL. Inpatient dose escalation is not allowed. In the dose escalation phase, once a given DL is cleared for DLT evaluation and is deemed safe, the dose cohort may be expanded (i.e., backfilled) to a maximum of 20 patients to further investigate the safety, PK, pharmacodynamic, and clinical activity. Enrollment of patients to the dose cohort for DLT evaluation/dose escalation will take precedent. To ensure that patients are not unnecessarily enrolled to subtherapeutic dose levels, these backfills will not be undertaken until a DL already declared safe also demonstrates evidence of therapeutic exposures. However, continuous safety monitoring (Section 9.2) will be implemented to ensure ongoing evaluation of patient safety in backfill patients. In the event that backfill enrollment/escalation is paused, the aggregated safety data will be evaluated to determine if the dose level in question (and higher dose levels) should be permanently discontinued. In general, all available toxicity and PK data will be utilized, including DLT equivalents observed from backfill patients, to recommend an escalation/de-escalation decision, and to inform the selection of the RP2D.

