#### 4.1.1. Dose Escalation

Dose escalation of LY3475070 will be driven by the modified toxicity probability interval-2 (mTPI-2) method (Guo et al. 2017) where a pre-calculated decision table (Appendix 8) will guide the dose recommendations until the MTD is determined (e.g., when all planned patients have been tested, or when no higher candidate DL can be tested). Dose escalation decision will also take into consideration available PK and pharmacodynamic data from previous DLs. Although mTPI-2 allows flexible number of patients in each dosing cohort, a minimum of 3 evaluable patients are required for the DLT evaluation at each DL. The first patient of each DL (in Phase 1a) will be observed for 48 hours before additional patients are enrolled to that DL. Inpatient dose escalation is not allowed.

Like the 3+3 design, the mTPI-2 method incorporates prespecified escalation rules. In contrast, the mTPI-2 method is based on quantitative models that incorporate uncertainty into the decision rules, thereby allowing more precise RP2D selection. If 3 or 6 patients are enrolled in a cohort, the escalation rule parallels a traditional 3+3 design. However, it allows flexible number of patients in a cohort. For example, with 2 DLTs per 6 patients enrolled, the mTPI-2 would recommend staying at the current dose, as analogy to 1 DLT per 3 patients enrolled in 3+3 design; therefore, it allows more patients for a more precise estimate of the DLT rate at this DL.

Following a discussion between the Lilly CRP/CRS and the investigators, a more conservative dose selection may be applied to the next cohort (for instance, if PK/pharmacodynamics data suggest that further dose increase would not be expected to yield additional benefit). For

example, if the rule indicates “E” to escalate, the dose may stay at the current DL, be de-escalated to a lower level, or escalation may cease. In the mTPI-2, the cohort size is not fixed. However, each DL in this study will be tested with a minimum of 3 evaluable patients, unless the escalation rules dictate that the dose should be de-escalated (“D” or “DU”). Doses can be escalated, de-escalated, and re-escalated. If the dose decision was “DU,” the dose cannot be re-escalated to that level.

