This study is designed to identify a DL with a dose-limiting target toxicity rate of 30%. The mTPI-2 method considers an equivalence interval (EI) around the target toxicity rate. For this study, the EI is elicited to be (25%, 35%), resulting in the rules below.

Safety data, in particular DLTs, will be the primary criteria for the dose escalation. In addition, if available at the time of dose escalation decision, PK/pharmacodynamics results (for example,  $C_{max}$ , area under the concentration curve (AUC), pharmacodynamics results) will be used as secondary/supporting data for dose escalation.

Intermediate and/or higher dose as well as alternative schedules of administration will be explored if deemed necessary after discussion between Lilly and investigators and taking into account patient safety and PK/pharmacodynamics data. If needed, additional patients may be enrolled to further assess PK/pharmacodynamics or tolerability.

In order to be DLT-evaluable, patients must have received 75% of LY3475070 scheduled dose within the 28-day DLT period unless patients have a DLT qualifying event. For patients treated with the combination treatment, patients must have received 75% of LY3475070 and a minimum of 1 pembrolizumab infusion within the 28-day DLT period.

In the dose escalation phase, once a given DL is cleared for DLT evaluation and is deemed safe, the dose cohort may be expanded to further investigate the safety, PK, pharmacodynamic, and clinical activity of LY3475070 and the combination with pembrolizumab. There will be up to 20 backfill patients enrolled across all dose levels in cohorts A and B combined in the phase 1a study. Any AEs reported by those backfilled patients that meet the DLT criteria as defined in Section 6.1.1.1 and occur in the DLT period are considered DLT-equivalent toxicities (Section 6.1.1.2). The cumulative safety data from the cohorts previously declared safe and the current dose cohort under evaluation will be continuously monitored. A Bayesian toxicity monitoring rule will be implemented for DLT-equivalent toxicities added from backfill patients (Section 9.2). These aggregate safety data will be included in defining the RP2D.

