### 6.1.1. Definition of DLT and DLT-ET

#### 6.1.1.1. DLT

A DLT is defined as any of the events listed in the table below, if both of the following criteria are met:

- the event occurs during the DLT observation period (28 days) in Phase 1a, and
- the event cannot, in the opinion of the investigator, be definitely attributed to primary disease or extraneous causes, such as accident.

Patients who experience a DLT in the DLT observation period will be discontinued from study treatment.

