**6.1.1.2. DLT-ET**

A **DLT-equivalent toxicity (ET)** is any event listed in Section 6.1.1.1 occurring after the DLT observation period in Phase 1a or any cycle in Phase 1b.

A DLT-ET is an AE that meets the DLT criteria as defined above and occurs in any cycle other than the DLT assessment period (28 days for Cohorts A1 through A4 and B1 through B3). In addition to the DLT assessment period, available safety data beyond the DLT assessment period may also be taken into consideration prior to a decision to advance to the next DL or the determination of the RP2D.

Potential DLTs that are AEs, which are reasonably anticipated AEs for concomitant medication should be reviewed by the treating investigator and Lilly CRP/CRS before final determination as a DLT. Review and discussion may include additional participating investigators. Such review

may determine that confounding factors render the case to be not evaluable for the purposes of dose selection.

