### 9.3. Populations for Analyses

For purposes of analysis, the following populations are defined:

Population	Description
Entered	All participants who sign informed consent
DLT evaluable	All patients enrolled in the dose escalation phase (phase 1a) who either complete 3 weeks of follow-up and treatment or discontinue treatment prior to 3 weeks due to a DLT.
PK Evaluable	All enrolled patients who have at least 1 post baseline evaluable PK sample
Safety	All participants who take at least 1 dose of study treatment. Participants will be included in the treatment group corresponding to their initial dose of study treatment, even if it is not the treatment to which they were assigned. In the event of a treatment error, participants will be analyzed according to the treatment they actually received. “Enrolled” population also refers to the “Safety” population in this study.
Phase 1a	All patients assigned to a treatment cohort during the dose escalation portion of the study.
Phase 1b	All patients assigned to a treatment cohort during the dose expansion portion of the study.
CD73+	CD73+ by IHC

Abbreviations: DLT = dose-limiting toxicity; IHC = immuno-histochemistry; PK = pharmacokinetics.

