### 10.8. Appendix 8: Dose-Finding Algorithm of the Modified Toxicity Probability Interval-2 Method Showing Number of Patients Treated

$n = 20, p_T = 0.3, \epsilon_1 = 0.05, \epsilon_2 = 0.05$

**E**: Escalate to the next higher dose; **S**: Stay at the same dose; **D**: De-escalate to the previous lower dose; **DU**: De-escalate to the previous lower dose and the current dose will never be used again in the trial;

\* If at the first dose level, users can choose to early-terminate the trial or not based on their own discretion.

The number of patients dosed at a given DL is shown in the columns (X-axis), while the number of DLTs experienced is shown in the rows (Y-axis). The rules in this figure will be used for each DL evaluated; the patient numbers and DLTs do not carry over from cohort to cohort. By locating the intersection of the number of patients dosed and the number of DLTs, 1 of 4 predefined rules is used:

- E: Escalate the dose
- S: Stay at the same dose
- D: De-escalate the dose
- DU: De-escalate the dose due to unacceptable toxicity. The dose cannot be re-escalated to this DL at a future point in the escalation.

For example, within a cohort:

- If 1 of 3 patients experiences a DLT, stay at the same dose (see “S” in column 3, row 1). The fourth patient must be treated at the same DL.
- If 1 of 6 patients experiences a DLT, escalate the dose (see “E” at column 6, row 1).
- If 2 of 3 patients experience a DLT the dose to treat the next patient is de-escalated (see “D” at column 3, row 2).
- If 5 of 7 patients experience a DLT, the dose is determined to be unacceptably toxic, and the previous dose is defined as the MTD.

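### Protocol 9.3 makes patients DLT-evaluable at 3 weeks, against a 28-day DLT window and a 28-day SAP population; one patient counted differently can change an mTPI-2 decision

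*Protocol*

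**What the plan says.** Protocol 9.3 defines the DLT-evaluable population as Phase 1a patients "who either complete 3 weeks of follow-up and treatment or discontinue treatment prior to 3 weeks due to a DLT". It sets no dose percentage and no pembrolizumab condition.

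Elsewhere the window is four weeks. Protocol 4.1 states: "The dose limiting toxicity (DLT) observation period will be 28 days". Sections 6.1.1.1 and 6.1.1.2 use the same 28 days to define a DLT and a DLT-equivalent toxicity, and SAP 5.1.1 agrees.

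Protocol 4.1.1 gives its own evaluability rule: "patients must have received 75% of LY3475070 scheduled dose within the 28-day DLT period unless patients have a DLT qualifying event". For combination patients it adds at least one pembrolizumab infusion. SAP 5.1.3 repeats both conditions. SAP Table JZMA.6.1 asks for follow-up to day 28 together with no less than 75% of doses, or discontinuation for a DLT before day 28; it leaves out the infusion condition.

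On the decision rule, 4.1.1 says "a minimum of 3 evaluable patients are required for the DLT evaluation at each DL", while Appendix 8 tells the reader how to enter the table with different wording: "The number of patients dosed at a given DL is shown in the columns (X-axis").

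**The concern.** DLTs are the first-listed Phase 1a primary endpoint and the main criterion for escalation. The mTPI-2 table takes two inputs, DLTs and patients, and the MTD depends on an estimated rate nearest 30% and under 35%. If the documents disagree on who is a patient for this purpose, the same data can give two decisions.

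The 3 weeks in 9.3 equals the 21-day treatment cycle, not the DLT window, which suggests a carry-over. Under 9.3, a DLT-free patient who is lost or withdraws consent after day 21 counts as a complete non-event with up to 28 − 21 = 7 days, a quarter of the window, unobserved. Protocol section 7 bars contact after consent withdrawal unless the patient has expressly allowed it, so those days may never be recovered.

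The conflict can also run the other way. Read literally, three weeks of treatment can exclude a DLT-free patient with a short interruption who still reaches 75% by day 28.

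**Working it through.** **Who is affected.** With once-daily dosing, 75% of 28 doses is 0.75 × 28 = 21 doses.

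| DLT-free patient | Protocol 9.3 | Protocol 4.1.1 | SAP Table JZMA.6.1 |
|---|---|---|---|
| Fully dosed for 21 days, then lost | in | in (dose rule met; no follow-up minimum stated) | out |
| One dose missed, then lost after day 21 with 20/28 = 71% | in, if the missed dose is tolerated | out | out |
| Short interruption in the first 3 weeks, at least 75% by day 28, followed to day 28 | out on a literal reading | in | in |

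A patient who only stops treatment after three fully dosed weeks is not in dispute: AE collection continues ("During the 30-, 60-, and 90-day follow-up visits, collect all AEs/SAEs") and the 75% is already met.

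**Reproducing the plan's decisions.** The inputs, from Appendix 8 and 4.1.1, are a target of 0.30 and an equivalence interval of 0.25 to 0.35. I assumed a Beta(1,1) prior. With x DLTs in n patients the posterior is Beta(1+x, 1+n−x). The range outside the equivalence interval is cut into sub-intervals of width 0.10, truncated at 0 and 1. The decision is the interval with the largest posterior probability divided by its width (UPM): Stay if it is the equivalence interval, Escalate if below, De-escalate if above. The cut-off for unacceptable toxicity (DU) is not stated; I used P(rate > 0.30) > 0.95. The calculation returns all five worked examples in the protocol: 1/3 Stay, 1/6 Escalate, 2/3 De-escalate, 5/7 DU and 2/6 Stay.

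**Patients per level.** Cohort A: 12/4 = 3 to 24/4 = 6. Cohort B: 9/3 = 3 to 18/3 = 6.

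**One DLT-free patient in or out.** For n = 4 to 6, the changes among Escalate, Stay and De-escalate are:

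| Data | UPM 0.15–0.25 | UPM 0.25–0.35 | UPM 0.35–0.45 | Decision |
|---|---|---|---|---|
| 1/4 | 2.024 | 2.044 | 1.722 | Stay |
| 1/5 | 2.425 | 2.149 | 1.555 | Escalate |
| 2/5 | 1.221 | 1.835 | 2.056 | De-escalate |
| 2/6 | 1.698 | 2.241 | 2.158 | Stay |

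These four decisions do not depend on the DU cut-off. With 3 patients, 0/3 is Escalate, but removing one leaves 0/2, below the 3-patient minimum. Not every change matters: 1/3 and 1/4 are both Stay, and 1/5 and 1/6 are both Escalate.

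**MTD condition.** As observed proportions, 2/6 = 33.3% is under 35% and 2/5 = 40.0% is not. The documents do not name the estimator.

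**Probability of a clean 0/3.** Let the true 28-day DLT rate be p = 0.30, and let q be the chance that a DLT shows by the last day observed. With all three patients followed, P(0/3) = 0.70³ = 34.3%. With one patient last seen on day d, P(0/3) = 0.70² × (1 − q). DLT timing is not in the documents, so three assumptions are shown.

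| Assumed timing | q, d = 21 | P(0/3) | q, d = 27 | P(0/3) |
|---|---|---|---|---|
| 10% of DLTs in week 4, spread evenly | 0.3 × 0.9 = 0.270 | 35.8% | 0.3 × (0.9 + 0.1 × 6/7) = 0.2957 | 34.5% |
| Constant hazard | 1 − 0.7^(21/28) = 0.2347 | 37.5% | 1 − 0.7^(27/28) = 0.2910 | 34.7% |
| Uniform over 28 days | 0.3 × 21/28 = 0.225 | 38.0% | 0.3 × 27/28 = 0.2893 | 34.8% |

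**The case against.** The best defence is that 4.1.1, which sits in the dose-escalation section, governs escalation in practice, and that 9.3 is a list for analysis. For the fully dosed patient lost after day 21, 9.3 and 4.1.1 even agree, since 21 doses are exactly 75%; only the SAP table excludes that patient. This is correct, but limited. The agreement fails once a dose is missed. Section 4.1.1 sets no minimum follow-up, so it does not secure the 28-day window either. And the protocol and SAP populations still differ for a primary endpoint.

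A second point is that 9.3 does not itself discard DLTs. An event on days 22 to 28 still counts under 6.1.1.1, and a patient who completed the three weeks is in the 9.3 set. That stands, and no claim of missed DLTs is made here for patients who remain under observation.

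Third, the effect is small and conditional: the increases of 0.2 to 3.7 percentage points apply only when one of three patients leaves DLT-free in a particular week, and how often that happens is unknown. The MTD contrast also depends on the estimator. With Beta(1,1) posterior means, 2/6 gives 3/8 = 37.5% and 2/5 gives 3/7 = 42.9%, and both fail the 35% condition. Both points stand.

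Finally, escalation is not mechanical. The totality of safety data is reviewed, a more cautious choice than the table's is allowed, later data may be considered, and a Bayesian rule monitors DLT and DLT-equivalent events, mainly for backfill. These soften the consequence; none of them fixes the denominator.

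**Conclusion.** The concern holds. Protocol 9.3 conflicts with the 28-day DLT window and with SAP Table JZMA.6.1, and for patients with missed doses it can also conflict with 4.1.1. This is current protocol text. The SAP cannot serve as a later correction, because it was approved in October 2019 on amendment (a) and the current protocol was approved in September 2020.

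At the planned 3 to 6 patients per level, one patient classified differently is enough to change a decision at 1/4 versus 1/5 and at 2/5 versus 2/6, or to drop a level below the evaluable minimum. The decision changes rest on the mTPI-2 reconstruction, which matches every worked example. The probability shifts rest on assumed DLT timing and a true rate of 30%. The net direction of bias is not established. The size is modest, but the population for a primary endpoint in a first-in-human dose-finding trial is defined inconsistently, so this must be corrected.

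**What to change.** Adopt one DLT-evaluable definition in protocol 9.3, protocol 4.1.1, SAP 5.1.3 and SAP Table JZMA.6.1, built from terms already in the documents: follow-up through day 28 with at least 75% of scheduled LY3475070, plus at least one pembrolizumab infusion for combination patients (missing from the SAP table), or a DLT at any time in the 28 days. State that this set is the denominator for mTPI-2 decisions and for the MTD estimate, and change the Appendix 8 wording on patients dosed to match.

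The cost is text edits in the protocol and SAP. DLT-free patients not followed to day 28 would need replacing for the DLT evaluation; the documents do not allow their number to be estimated.

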### 9.4. Statistical Analyses

#### 9.4.1. General Statistical Considerations

Statistical analysis of this study will be the responsibility of Lilly or its designee.

Efficacy analyses will be conducted on the set of all enrolled patients. This set includes all data from all participants receiving at least 1 dose of the investigational product according to the treatment the participants were assigned.

All tests of treatment effects will be conducted at a 1-sided 0.05 alpha level, as appropriate for the comparison, unless otherwise stated.

Any change to the data analysis methods described in the protocol will require an amendment ONLY if it changes a principal feature of the protocol. Any other change to the data analysis methods described in the protocol, and the justification for making the change, will be described in the clinical study report (CSR). Additional exploratory analyses of the data will be conducted as deemed appropriate.

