### **9.4.3. Efficacy Analyses**

#### **9.4.3.1. Primary Analyses**

Overall response rate is defined as the number of patients who achieve a best overall response of CR or PR divided by the total number of patients treated (safety population). The ORR, with 95% CI, will be summarized for each study part.

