DLT evaluable	All patients enrolled in the dose escalation phase (Phase 1a) who either complete 28 days of follow-up and at least 75% of treatment doses or discontinue treatment prior to 28 days due to a DLT.
Randomized	(Phase 1b portion only). All patients in cohorts C and D who are randomized to a treatment regimen, regardless of whether they take any study drug.
PK evaluable	All enrolled patients who have at least 1 postbaseline evaluable PK sample.
Safety	All participants who take at least 1 dose of study treatment. Participants will be included in the treatment group corresponding to their initial dose of study treatment, even if it is not the treatment to which they were assigned. In the event of a treatment error, participants will be analyzed according to the treatment they actually received. “Enrolled” population also refers to the “Safety” population in this study.
Screen Failures	Patients who have signed informed consent, do not meet eligibility criteria and are not enrolled.

Abbreviations: DLT = dose-limiting toxicity; PK = pharmacokinetic(s).

Any change to the data analysis methods described in the protocol/SAP will require an amendment ONLY if it changes a principal feature of the protocol/SAP. Any other change to the data analysis methods described in the protocol/SAP, and the justification for making the change, will be described in the clinical study report. Additional exploratory analyses will be conducted as deemed appropriate.

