6.7. Efficacy Analyses

The antitumor activity of LY3475070 monotherapy and in combination with pembrolizumab will be assessed based on RECIST 1.1 and iRECIST (Seymour et al. 2017), respectively. The

efficacy analyses will be focused on treated participants (safety populations) in Phase 1a part of the study (dose escalation), and in Phase 1b part of the study (dose expansion).

The Kaplan-Meier method (Kaplan and Meier 1958) will be used to estimate the curves, median time and 95% CI of time to event parameters such as OS, PFS and DoR based on RECIST 1.1, iPFS and iDOR based on iRECIST for each arm of Cohorts C and D, and Cohort E. Overall response rate (ORR based on RECIST 1.1 and iORR based on iRECIST), with corresponding 95% exact CI, will be summarized for each arm of Cohorts C and D, and Cohort E. ORR with corresponding 95% exact CI will also be summarized for the monotherapy and combination cohorts in Phase 1a part of the study.

The following definitions for efficacy endpoints will be used:

Primary Endpoint

Overall response rate (ORR) is defined as the number of patients who achieve a best overall response of complete response (CR) or partial response (PR) divided by the total number of patients treated (safety population). The ORR, with 95% CI, will be summarized for each study part.

Secondary Endpoints

The **disease control rate (DCR)**, defined as the proportion of patients who achieved a CR or PR or stable disease (SD) out of all patients treated, will also be summarized. Best response is determined from a sequence of responses assessed. Two objective status determinations of CR before progression are required for a best response of CR. Two determinations of PR or better before progression, but not qualifying for a CR, are required for a best response of PR.

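### For response rate in randomised Cohorts C and D, Protocol 9.4.1 places dosed patients by assigned arm, while Protocol 9.4.3.1 and SAP 6.7 place them by treatment received.

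*Protocol*

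**What the plan says.** **By assignment.** Protocol 9.4.1 states: "Efficacy analyses will be conducted on the set of all enrolled patients". It then describes that set as the data from "participants receiving at least 1 dose of the investigational product according to the treatment the participants were assigned".

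**By treatment received.** Protocol 9.4.3.1 defines the response rate as the number of responders "divided by the total number of patients treated (safety population", the Safety population being named there in brackets. SAP 6.7 agrees: "efficacy analyses will be focused on treated participants (safety populations) in Phase 1a part of the study", and the sentence goes on to say the same of Phase 1b. SAP 6.7 also puts iORR on the Safety population.

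Protocol 9.3 places Safety patients by their initial dose, "even if it is not the treatment to which they were assigned", and adds that after a treatment error "participants will be analyzed according to the treatment they actually received". SAP Table JZMA.6.1 carries the same rule: "Participants will be included in the treatment group corresponding to their initial dose of study treatment".

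**The shared label.** Protocol 9.3 and SAP Table JZMA.6.1 both say that Enrolled is another name for the Safety population. Enrolled is the label that Protocol 9.4.1 gives to its by-assignment set. The glossary in Protocol Appendix 9 gives a third meaning: enrolled patients are those who have been assigned to a treatment.

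**The Randomized set.** SAP Table JZMA.6.1 also defines a set of Cohort C and D patients "who are randomized to a treatment regimen, regardless of whether they take any study drug". Protocol 9.3 has no such set.

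**The concern.** Investigator-assessed response rate is a primary endpoint of Phase 1b. SAP 6.7 reports it separately for each arm of Cohorts C and D. Two rules decide which arm a patient belongs to, both can claim the word enrolled, and nothing says which prevails. Two analysts following the documents faithfully could report different per-arm rates from the same data.

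Protocol 6.3 says that these cohorts are randomised to mitigate selection bias in an open-label study. Placing patients by what they received gives up that protection for any patient whose first treatment differs from the allocation. The arms are small, and the per-arm results feed the interim decision in Protocol 9.5 on adding 20 patients to the combination arm, so a single patient is visible in the result.

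**Working it through.** **1. The rules side by side**

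| Place | Patients | Arm decided by |
|---|---|---|
| Protocol 9.4.1 (efficacy) | at least 1 dose | assignment |
| Protocol 9.4.3.1 (ORR), using 9.3 | at least 1 dose | first dose or treatment received |
| SAP 6.7 (efficacy, ORR, iORR), using Table JZMA.6.1 | at least 1 dose | first dose or treatment received |
| SAP Table JZMA.6.1, Randomized | all randomised in C and D | no analysis names it in the legible text |

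The first three rows contain the same patients. They disagree only on the arm of a dosed patient who started on the wrong treatment. The conflict lies within the protocol, and between Protocol 9.4.1 and the SAP.

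**2. Check of the interval method**

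The plan gives no figure for this point. The nearest is the precision table in Protocol 9.2, which uses Clopper-Pearson limits. For x responders among n patients:

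- lower limit = the 0.025 quantile of Beta(x, n − x + 1), or 0 if x = 0
- upper limit = the 0.975 quantile of Beta(x + 1, n − x)

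The limits in all ten rows of that table reproduce. For example, 0/20 gives 0 to 0.168 (stated 0.17), 5/20 gives 0.087 to 0.491 (stated 0.09 and 0.49), and 10/40 gives 0.127 to 0.412 (stated 0.13 and 0.41).

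**3. What one misallocated patient does**

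From Protocol 9.5: 10 monotherapy and about 20 combination patients at the interim. Assumed for illustration: 1 monotherapy and 4 combination responders by assignment, and one monotherapy-assigned patient who is dosed with the combination.

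| Case | Monotherapy | Combination | Difference |
|---|---|---|---|
| By assignment | 1/10 = 10% (0.3 to 44.5%) | 4/20 = 20% (5.7 to 43.7%) | 10 points |
| As received, moved patient is the responder | 0/9 = 0% (0 to 33.6%) | 5/21 = 23.8% (8.2 to 47.2%) | 23.8 points |
| As received, moved patient is a non-responder | 1/9 = 11.1% (0.3 to 48.2%) | 4/21 = 19.0% (5.4 to 41.9%) | 7.9 points |

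The cohort total is unchanged by the move. For the responder, 1 + 4 = 0 + 5 = 5 responses among 10 + 20 = 9 + 21 = 30 patients.

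**4. Undosed patients, taken separately**

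A patient who is randomised but never dosed is outside every efficacy rule in step 1, so the conflict does not involve such patients. If they were added to the denominator, 4/20 would become 4/21 (19.0%) with one undosed patient or 4/22 (18.2%) with two, and 1/10 would become 1/11 (9.1%).

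Protocol 9.4.2.1 counts patients entered, enrolled and treated. If Enrolled means Safety, as in 9.3, the last two counts coincide. SAP 6.3 counts patients entered and treated. Neither promises a count of undosed patients by arm, although Protocol 7.3 has sites seek vital status for randomised patients who never received product.

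**The case against.** The strongest reply is that the conflict will rarely bite. Both arms take LY3475070 and differ only by pembrolizumab, which authorised staff infuse at the site (Protocol 6.1 and 6.4). A conflict needs an infusion wrongly given or omitted at first dosing, and the documents give no reason to expect more than isolated cases. Protocol 9.1 plans no formal test of response rate, and the intervals in the working overlap heavily. Expansion rests on the totality of efficacy, safety and PK/pharmacodynamic data. The rule in Protocol 9.5 for not continuing when there are no responses, read as none in either arm, depends on the cohort total, which regrouping leaves alone. All of this stands. It limits the size of the problem but does not say which rule applies.

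Three stronger readings are tempting, and the documents do not support them.

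- **Lost patients.** A reader might infer that the conflict lets patients drop out unseen, for example those who withdraw on learning that they drew monotherapy. Protocol 9.4.1 also requires at least one dose, so such patients are absent under both rules, and aligning the sections would not bring them back. Nor are they wholly invisible: Protocol section 7 collects discontinuation reasons for all patients.
- **A set that is never used.** A reader might say this of the Randomized set. It can be said only of the legible text, because SAP 6.10 is partly redacted. The SAP does use the date of randomisation, as the origin for iPFS, but without naming the set.
- **A wrong Safety definition.** Placing patients by treatment received suits safety analyses. The fault is in carrying that rule into efficacy.

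**Conclusion.** The contradiction is real and worth correcting. For a Phase 1b primary endpoint in the two randomised cohorts, the plan holds two incompatible rules for placing a misallocated patient in an arm.

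In the illustration, one such patient among 30 changes the between-arm difference from 10 points to 23.8 (a responder) or 7.9 (a non-responder). These figures rest on assumed response counts, one assumed misallocation and the approximate arm sizes at the interim. The documents give no frequency for misallocation, and with none the two rules give identical results.

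The consequence is bounded because response rate is estimated and not formally tested. No sample size or other stated figure is affected. The missing by-arm count of undosed randomised patients is a separate and minor gap in reporting.

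**What to change.** - In Protocol 9.4.3.1 and SAP 6.7, state that efficacy in Cohorts C and D is analysed in dosed patients by randomised arm, in line with Protocol 9.4.1. Apply this to every efficacy endpoint reported by arm.
- Keep grouping by treatment received for safety analyses only. The Safety definition in Protocol 9.3 and SAP Table JZMA.6.1 can stay. Remove the statement that Enrolled means Safety, or limit it so that it does not carry the as-received rule into efficacy, and reconcile it with the glossary.
- Separately, use the SAP's Randomized set to show randomised but undosed patients by arm in the disposition table. A supportive response-rate line with all randomised patients as denominator is optional.

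The cost is a few sentences and one table line, with no new patients or data. SAP Version 1 is based on protocol amendment (a), and the protocol now stands at amendment (d), so the wording could go into an SAP update.
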